6.1.4.12 HEMORRAGIC EVENTS

Hemorrhagic events have been reported with approved drugs that inhibit VEGF pathways as well as with cabozantinib. In order to mitigate risk of severe hemorrhage, subjects should be evaluated for potential bleeding risk factors prior to initiating study treatment and monitored for bleeding events with serial complete blood counts and physical examination while on study. Risk factors for hemorrhagic events may include (but may not be limited to) the following:

- Tumor of the lung with cavitary lesions or tumor lesions which invades, encases, or abuts major blood vessels. The anatomic location and characteristics of tumor as well as the medical history must be carefully reviewed in the selection of subjects for study treatment.
- Recent or concurrent radiation
- Active peptic ulcer disease, ulcerative colitis, and other inflammatory GI diseases
- Underlying medical conditions which affect normal hemostasis (eg, deficiencies in clotting factors and/or platelet function, or thrombocytopenia)
- Concomitant medication with anticoagulants or other drugs which affect normal hemostasis
- History of clinically significant hemoptysis

Discontinue study treatment in subjects who experience a severe bleeding complication.

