6.1.4 DOSE MODIFICATIONS

6.1.4.1 CABOZANTINIB DOSE MODIFICATIONS

Cabozantinib dose reduction

Toxicities will be graded using the NCI CTC version 5.0 (see Appendix 4). All dose modifications will follow pre-defined dose levels as indicated below.

The modifications of cabozantinib dosage will follow the following pre-defined dose levels:

Table 1: Cabozantinib dose reduction

| | | |
|------------------------------|----------|--|
| Dose level 0 (standard dose) | 60 mg po | 1 tablet of cabozantinib every day |
| Dose level -1 | 40 mg po | 1 tablet of cabozantinib every day |
| Dose level -2 | 20 mg po | 1 tablet of cabozantinib every day |
| Dose level -3 | 20 mg po | 1 tablet of cabozantinib every 2 or 3 days |

If a patient experiences several toxicities and there are conflicting recommendations, the recommended dose adjustment, which reduces the dose to the lowest level, should be used.

If a dose reduction has been performed, intra-subject dose re-escalation can be considered (up to the maximum of 60 mg daily dose) at the discretion of the treating investigator provided that the toxicities has resolved to at least CTC-Grade baseline levels.

Table 2 Dose Modification Criteria

| Toxicity | Criteria Recommended Guidelines for Management |
|---|--|
| Grade 1 AEs | Continue study treatment if AE is tolerated |
| Grade 2 AEs which are intolerable and cannot be adequately managed | At the discretion of the investigator, study treatment should be dose reduced or interrupted. Note: It is recommended that dose interruptions be as brief as possible. |
| Grade 3 (except clinically non-relevant laboratory abnormalities) | Study treatment should be interrupted unless the toxicity can be easily managed with a dose reduction and optimal medical care. |
| Grade 4 AEs (except clinically non-relevant laboratory abnormalities) | Subjects should have their study treatment interrupted immediately. Discontinue study treatment unless the following criteria are met: Subject is deriving clear clinical benefit as determined by the investigator and agreed by the Sponsor. Toxicity can be managed with a dose reduction following recovery to Grade 1 (or baseline) and optimal medical care |

AE, adverse event.

^a Study treatment dose adjustment is only needed if the toxicity was deemed related to study treatment or had an unclear relationship to study treatment.

^b For dose reduction levels, see Table 1.

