6.1.4.9 THROMBOEMBOLIC EVENTS

Thromboembolic complications are frequent in cancer patients due to procoagulant changes induced by the malignancy or anticancer therapy including inhibitors of VEGF pathways. DVT and PE have been observed in clinical studies with cabozantinib; including fatal events (please refer to the Investigator's Brochure). Subjects who develop a PE or DVT should have study treatment held until therapeutic anticoagulation with heparins (LMWH) is established. (Note: therapeutic anticoagulation with oral anticoagulants is prohibited.) Study treatment may be resumed in subjects with PE or DVT if it is determined that the event is uncomplicated, they are deriving benefit from study treatment, and that anticoagulation does not place them at a significant risk that outweighs the benefit of resuming treatment. During treatment with anticoagulants, subjects need to be monitored on an ongoing basis for bleeding risk and signs of bleeding. Subjects with life-threatening PE or DVT should have study treatment discontinued unless toxicity can be managed and subject is deriving clear clinical benefit as

determined by the investigator. Subjects who develop portal/hepatic vessel thrombosis may not require anticoagulation. The decision regarding anti-coagulation in such cases is at the discretion of the investigator and within the context of standard of care. Arterial thrombotic events (eg, transient ischemic attack, myocardial infarction) have been observed rarely in studies with cabozantinib. Subjects should be evaluated for preexisting risk factors for arterial thrombotic events such as diabetes mellitus, hyperlipidemia, hypertension, coronary artery disease, history of tobacco use, and cardiac or thromboembolic events that occurred prior to initiation of study treatment. Study treatment should be discontinued in subjects who develop an acute myocardial infarction or any other clinically significant arterial thromboembolic complication.

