6.1.4.13 GI PERFORATION/FISTULA AND NON-GI FISTULA FORMATION

GI perforation/fistula and non-GI fistula formation have been reported with approved drugs that inhibit VEGF pathways as well as with cabozantinib. Carefully monitor for episodes of abdominal pain, especially in subjects with known risk factors for developing GI perforation/fistula or non-GI fistula, to allow for early diagnosis. Such risk factors include (but may not be limited to) the following:

GI perforation/fistula:

- Intra-abdominal tumor/metastases invading GI mucosa
- Active peptic ulcer disease, inflammatory bowel disease, ulcerative colitis, diverticulitis, cholecystitis or symptomatic cholangitis, or appendicitis
- History of abdominal fistula, GI perforation, bowel obstruction, or intra-abdominal abscess
- Prior GI surgery (particularly when associated with delayed or incomplete healing).

Complete healing following abdominal surgery or resolution of intra-abdominal abscess must be confirmed prior to initiating study treatment.

Additional risk factors include concurrent chronic use of steroid treatment or nonsteroidal anti-inflammatory drugs. Constipation indicative of bowel obstruction should be monitored and effectively managed.

Non-GI fistula:

- Complications from radiation therapy have been identified as a possible predisposing risk factor for non-GI fistula formation in subjects undergoing treatment with VEGF pathway inhibitors (eg, bevacizumab). Subjects are excluded from this study if there are any clinically relevant ongoing complications from prior radiation therapy (ie, radiation esophagitis or other inflammation of the viscera).

Discontinue all study treatment in subjects who have been diagnosed with GI or non-GI perforation/fistula.

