6.1.6 PERMANENT DISCONTINUATION OF CABOZANTINIB DUE TO ADVERSE EVENTS

Cabozantinib administration should be discontinued if at least one of the following drug-related adverse event(s) occurs:

- Subject no longer experiences clinical benefit as determined by the investigator. If study treatment is withdrawn for this reason, the date of this decision is to be recorded and every effort should be made to continue safety evaluations and collection of subsequent treatment information and follow-up information for survival.
- Unacceptable side effects the investigator feels may be due to study treatment, including any subject with a GI or non-GI perforation/fistula
- Any adverse event, laboratory abnormality or intercurrent illness, which, in the judgment of the Investigator, presents a substantial clinical risk to the subject with continuing study medication.
- Any Grade 3 non-skin, drug-related adverse event lasting $>$ 21 days
Exception of grade 3 drug-related AE:
 - Grade 3 drug-related laboratory abnormalities do not require treatment discontinuation except:
- Any drug-related Grade 4 drug-related adverse event or laboratory abnormality, except for the following events which do not require discontinuation:
 - Grade 4 neutropenia $<$ 7 days;

- Grade 4 lymphopenia or leukopenia;
- Grade 4 amylase or lipase abnormalities that are not associated with symptoms or clinical manifestations of pancreatitis;
- Isolated Grade 4 electrolyte imbalances/abnormalities that are not associated with clinical sequelae and are corrected with supplementation/appropriate management within 72 hours of their onset;
- The investigator feels it is not in the best interest of the subject to continue on study
- Participation in another clinical study using an investigational agent or investigational medical device
- Necessity for treatment with non-protocol systemic anticancer therapy
- Receipt of liver-directed local anti-cancer therapy (eg, transarterial tumor embolization or chemoembolization, radiofrequency or microwave ablation, percutaneous ethanol or acetic acid ablation, injection or infusion of drug eluting or radiation-emitting beads, cryoablation, radiation therapy, including stereotactic radiotherapy, or surgery)
- Necessity for withholding study drug for greater than 8 weeks for AEs, unless continuation of treatment is approved by the Principal Investigator

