- Refusal of sexually active fertile subjects (excluding subjects who have been sterilized) to use medically accepted methods of contraception
- Pregnancy of a female subject
- Request by the Principal Investigator
- Subject request to discontinue study treatment
- Significant noncompliance with the protocol schedule in the opinion of the investigator or the Principal Investigator
- The Principal Investigator should be notified of all discontinuations of study treatment as soon as possible. If a subject fails to return for the protocol-defined visits, an effort must be made to determine the reason. If the subject cannot be reached by telephone, at a minimum, a registered letter should be sent to the subject (or the subject's legal guardian) requesting contact with the study site.
- For subjects who withdraw or are withdrawn from study treatment, every effort must be made to continue protocol-specified evaluations and procedures through the post-treatment follow-up and extended follow-up visits unless consent to participate in the study is also withdrawn. All subjects will be followed until death, unless consent to do so is specifically withdrawn by the subject or until a decision by the Principal Investigator is made to stop collection of these data.

If the Investigator consider the option of continue with one of the investigations drugs, the decision to continue with one of the drug-study treatments beyond the criteria mentioned in this point of the protocol should be discussed with the Principal Investigator, Medical Monitor and documented in the study records.

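### Severe bleeding and arterial thromboembolism are unconditional stops in Protocol 6.1.4.12 and 6.1.4.9 but interrupt-or-reduce events in Table 2, and no sentence says which rule governs

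*Protocol*

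**What the plan says.** **Event-specific sections.** For bleeding, Protocol 6.1.4.12 says "Discontinue study treatment in subjects who experience a severe bleeding complication". For arterial events, 6.1.4.9 says "Study treatment should be discontinued in subjects who develop an acute myocardial infarction or any other clinically significant arterial thromboembolic complication". For perforation, 6.1.4.13 says "Discontinue all study treatment in subjects who have been diagnosed with GI or non-GI perforation/fistula". None of the three sentences mentions relatedness or resumption.

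**General table.** For Grade 3, Table 2 in 6.1.4.1 says "Study treatment should be interrupted unless the toxicity can be easily managed with a dose reduction and optimal medical care". For Grade 4 it requires immediate interruption and then "Discontinue study treatment unless the following criteria are met"; the criteria are clear benefit agreed by the sponsor and toxicity manageable at a reduced dose after recovery. Its footnote a adds "Study treatment dose adjustment is only needed if the toxicity was deemed related to study treatment or had an unclear relationship to study treatment". Section 6.1.5 gives the conditions for resuming.

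**Permanent-discontinuation list.** Section 4.1.4, the list of mandatory stops, refers to 6.1.6 for specific criteria and does not cite 6.1.4.9, 6.1.4.12 or 6.1.4.13. Section 6.1.6 opens "Cabozantinib administration should be discontinued if at least one of the following drug-related adverse event(s) occurs". It names perforation or fistula in any subject. It does not name bleeding or arterial events. It lists Grade 3 non-skin drug-related events only when they last more than 21 days, and it lists drug-related Grade 4 events with a few exceptions (certain blood-count, enzyme and electrolyte abnormalities). Its closing paragraph leaves a way to continue, under which "the decision to continue with one of the drug-study treatments beyond the criteria mentioned in this point of the protocol should be discussed"; both the Principal Investigator and the Medical Monitor take part, and a record must be kept.

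**Outcome.** The rate of AEs leading to treatment discontinuation is a primary outcome in Protocol 9.1 and SAP 8.3.1.

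**The concern.** These are serious vascular events for which the protocol writes plain stop instructions. A site that opens the bleeding section stops the drug. A site that works from Table 2, or that follows 4.1.4 to 6.1.6, can interrupt and restart, and may never meet the bleeding or arterial sentence.

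Two things are at stake. The first is consistent handling of a patient-safety stop across the seven planned sites. The second is that a listed primary outcome counts discontinuations, so its rate would partly record which section a site followed rather than how the drug was tolerated.

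**Working it through.** The plan has no figure of its own to reproduce on this point. The check sets the rules side by side by event, grade and relatedness, and then sizes the effect on the discontinuation rate.

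**Step 1: what counts as severe.** Protocol 8.3.2 labels Grade 3 as severe. SAP 8.6.5.3.7 treats Grade 3 or higher as severe. A Grade 3 bleed therefore falls under 6.1.4.12.

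**Step 2: the rules compared.**

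| Event | Event-specific section | Table 2 | Section 6.1.6 | Result |
|---|---|---|---|---|
| Grade 3 bleed or arterial event, drug-related, resolving within 21 days | Discontinue | Interrupt or reduce; 6.1.5 then governs resuming | No stop, unless the investigator judges otherwise | Conflict with both |
| Grade 4 bleed or arterial event, drug-related | Discontinue | Interrupt; may continue under conditions | Discontinue (not among the exceptions) | Table 2 is the outlier |
| Bleed or arterial event judged unrelated | Discontinue (silent on cause) | Footnote a: dose adjustment not needed | Outside the drug-related opening line, unless investigator judgement applies | Conflict, on a literal reading |
| Perforation or fistula | Discontinue | Depends on grade, as above | Discontinue, any subject | 6.1.4.13 and 6.1.6 agree; Table 2 differs |

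**Step 3: is there a tie-break?** The only one, in 6.1.4.1, applies when a patient has several toxicities with conflicting recommendations. It does not cover one toxicity that falls under two rules.

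**Step 4: can the closing paragraph of 6.1.6 change a stop?** By its terms it concerns the criteria of 6.1.6. That includes the perforation item and the drug-related Grade 4 item. Sections 6.1.4.9, 6.1.4.12 and 6.1.4.13 contain no such route, and the text does not say whether the paragraph extends to them.

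**Step 5: size.** Planned n = 40 (Protocol 9.2). One patient handled differently moves the discontinuation rate by 1/40 = 2.5 percentage points. The documents give no rate for these events in HCC. Assuming that 1 to 3 of 40 patients are affected, the shift is 2.5 to 7.5 points (3/40 = 7.5%).

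As an illustration, with assumed counts and the Clopper-Pearson method of SAP 8.6.5.1 (lower limit is the 0.025 quantile of Beta(x, n − x + 1), upper limit is the 0.975 quantile of Beta(x + 1, n − x)):

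- 6/40 = 15.0% (95% CI 5.7 to 29.8)
- 8/40 = 20.0% (95% CI 9.1 to 35.6)

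**Step 6: does the sample-size outcome move?** That outcome is CTCAE Grade 3 or higher, excluding palmar-plantar erythrodysesthesia. A patient with a Grade 3 or higher bleed, arterial event or perforation already counts, whether the drug is then stopped or continued. Counted per patient, the outcome does not change.

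**The case against.** The strongest reply is that the specific section overrides the general table. Table 2 is presented as recommended guidance. Sections that rely on it say so (diarrhea in 6.1.4.3, hepatobiliary in 6.1.4.4), while 6.1.4.9, 6.1.4.12 and 6.1.4.13 state their own action and do not mention it. Section 6.1.6 says to stop if an item occurs, not only if one does, so its silence on bleeding does not license continuing. Its opening line is loose, since the list goes on to pregnancy and subject request. Both 4.1.4 and 6.1.6 also allow a stop on investigator judgement. This is a sensible reading and may be what was intended, but the protocol does not state it, and 4.1.4 points away from the event-specific sections.

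Several stronger readings are tempting, and the documents do not support them:

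- **That 6.1.6 lets a perforation patient carry on.** It names any such subject as a stop. The closing paragraph requires discussion with the Principal Investigator and Medical Monitor, so it is not a free site choice.
- **That the event-specific stops apply whatever the cause.** The sentences are silent on cause; they do not say it is irrelevant. The drafting gives some support, because the palmar-plantar and hypertension guidance (6.1.4.7, 6.1.4.8) does state relatedness. It remains an inference.
- **That footnote a means no action for an unrelated bleed.** It speaks of dose adjustment, and the table as extracted shows no anchor for it, so the rows it governs cannot be established.
- **That longer exposure alters the critical-AE result.** Such a patient already counts, as shown above.

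The events may also be few. Section 5.2.1 excludes recent ischemic events, recent significant bleeding and inadequately treated varices, although patients with adequately treated varices are eligible.

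**Conclusion.** The contradiction is real for severe bleeding and clinically significant arterial thromboembolism. At Grade 3, the event-specific sections differ from both Table 2 and 6.1.6. At drug-related Grade 4, they and 6.1.6 agree and Table 2 stands apart. For perforation or fistula the gap is narrower: Table 2, and whether the closing paragraph of 6.1.6 can apply.

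The statistical effect is modest. It is 2.5 points per affected patient on a primary outcome that SAP 8.5 calls non-confirmatory and SAP 8.6 analyses without inference. The two illustrative intervals overlap heavily. The range of 1 to 3 patients is an assumption, and it also assumes that each would be handled differently under the other rule. The sample-size outcome and the interim rule do not move, provided that critical AEs are counted per patient.

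The main reason to act is that safety stop rules contradict each other on the page. That does not depend on the assumed counts. Nothing here says which rule is clinically right.

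**What to change.** In the next protocol amendment:

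1. Reconcile 6.1.4.9 and 6.1.4.12 with Table 2 (including footnote a), 6.1.5 and 6.1.6, so that each event and grade has one stated action.
2. For bleeding, arterial events and perforation or fistula, state whether relatedness matters and whether the closing paragraph of 6.1.6 applies.
3. Have 4.1.4 and 6.1.6 cite 6.1.4.9, 6.1.4.12 and 6.1.4.13.
4. Add one sentence saying which section prevails when a single event falls under two.

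The clinical content of each rule is for the sponsor to decide. The cost is protocol wording and a note to sites, with no extra patients or procedures.

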6.1.4.13 GI PERFORATION/FISTULA AND NON-GI FISTULA FORMATION

GI perforation/fistula and non-GI fistula formation have been reported with approved drugs that inhibit VEGF pathways as well as with cabozantinib. Carefully monitor for episodes of abdominal pain, especially in subjects with known risk factors for developing GI perforation/fistula or non-GI fistula, to allow for early diagnosis. Such risk factors include (but may not be limited to) the following:

GI perforation/fistula:

- Intra-abdominal tumor/metastases invading GI mucosa
- Active peptic ulcer disease, inflammatory bowel disease, ulcerative colitis, diverticulitis, cholecystitis or symptomatic cholangitis, or appendicitis
- History of abdominal fistula, GI perforation, bowel obstruction, or intra-abdominal abscess
- Prior GI surgery (particularly when associated with delayed or incomplete healing).

Complete healing following abdominal surgery or resolution of intra-abdominal abscess must be confirmed prior to initiating study treatment.

Additional risk factors include concurrent chronic use of steroid treatment or nonsteroidal anti-inflammatory drugs. Constipation indicative of bowel obstruction should be monitored and effectively managed.

Non-GI fistula:

- Complications from radiation therapy have been identified as a possible predisposing risk factor for non-GI fistula formation in subjects undergoing treatment with VEGF pathway inhibitors (eg, bevacizumab). Subjects are excluded from this study if there are any clinically relevant ongoing complications from prior radiation therapy (ie, radiation esophagitis or other inflammation of the viscera).

Discontinue all study treatment in subjects who have been diagnosed with GI or non-GI perforation/fistula.

6.1.4.14 OSTEONECROSIS OF THE JAW

Osteonecrosis of the jaw (ONJ) has been reported with use of anti-angiogenic drugs and bisphosphonates and denosumab in cancer patients. Additional risk factors for ONJ have been identified such as use of corticosteroids, chemotherapy, local radiotherapy, poor oral hygiene, smoking, dental or orofacial surgery procedures, and cancer disease itself. Osteonecrosis has been reported in subjects treated with cabozantinib, the details of which are provided in the current version of Investigator's Brochure. As a preventive measure, invasive dental procedures should be avoided if possible. In cases where dental procedures are unavoidable, the risks and benefits of a dental procedure and the extent of the procedure as well as the risk of developing osteonecrosis of the jaw need to be considered when deciding on the duration of a temporary study treatment interruption. If clinically possible, study treatment should be held for approximately 4 weeks prior to a dental procedure and resumed after complete healing has occurred.

Subjects with any documented case of osteonecrosis should have study treatment interrupted, and appropriate clinical management should be initiated. Re-initiation of study treatment must be discussed with and approved by the Principal Investigator of the study.

6.1.5 CRITERIA TO RESUME CABOZANTINIB TREATMENT

Subjects may resume treatment with cabozantinib when the drug-related AE(s) resolve to Grade \leq 1 or baseline value, with the following exceptions:

- Subjects may resume dosing in the presence of Grade 2 fatigue
- Subjects who delayed dosing due to UPCR \geq 2.0 or urine dipstick protein \geq 3+ may resume dosing at one dose level reduction when 24 hours urine protein $<$ 2.0 g or repeat UPCR $<$ 2.0
- Subjects who delayed dosing due to Grade 3 hypertension may resume dosing at the same dose or at one dose level reduction, at the discretion of the investigator, when hypertension has improved to Grade \leq 2.
- Subjects who delayed dosing due to Grade 4 lipase abnormalities (either asymptomatic or in the absence of radiographic findings) may resume dosing upon resolution to Grade \leq 2.
- Subjects who delayed dosing due to major surgery should not resume cabozantinib until complete wound healing has taken place. Following cabozantinib resumption, subjects should be monitored for wound dehiscence, wound infections, and other signs of impaired wound healing.

If treatment is delayed 8 weeks for any reason, the participant must be permanently discontinued from study therapy, except in cases where permission to resume treatment is granted by the Medical Monitor or designee.

